**Hypothesis 1:** Chronic inflammation inhibition will improve microvascular and large elastic artery function in obese adults with prediabetes.

**Aim 2:** To measure muscle sympathetic nervous system activity (MSNA) and baroreflex sensitivity in obese prediabetic adults before and after 1 month of salsalate or placebo.

**Hypothesis 2:** Chronic inflammation inhibition will decrease MSNA and improve baroreflex sensitivity in obese adults with prediabetes.

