#### **DESCRIBE:**

- What subjects will be asked to do/what happens in the study (in sequential order)
- The time period over which procedures will occur
- The time commitment for the subject for individual visits/procedures
- Long-term followup and how it occurs

Experimental design. A total of 30 obese (defined as body mass index >30 kg/m2) adults age 18-49 years with prediabetes will be enrolled and randomized to 4-5 weeks of Salsalate or placebo in a randomized (2:1), double-blind, placebo controlled, parallel study design. Subjects will orally ingest 3000 mg/day (1500 mg in a.m. and 1500mg in the p.m.) of Salsalate (n=20) or placebo (n=10) for 28-35 days. A total of n=10 obese NON-prediabetic CONTROL subjects will be enrolled to establish prediabetes-related differences in obese adults primary outcomes at baseline. Therefore, a total of 40 subjects will be enrolled. The non-prediabetic control subjects will undergo screening (Visits 1 and 2) and baseline experimental testing (Visits 3, 4) but will NOT undergo the Salsalate/placebo intervention or visits 5, 6 or 7. Prediabetes will be defined as fasting (at leaset 8 hour fast) blood glucose between 100-126 mg/dl, a fasting blood glucose of 140-199 mg/dl at 120 min during an oral glucose tolerance test, or HbA1C between 6.0 – 6.5%.

Order of visits. Subjects will undergo experimental testing at baseline and again after the 4-5 weeks of Salsalate or placebo. Subjects will be studied between 7:00 and 10:00 am in the Clinical Research Unit (CRU) in the Institute for Clinical and Translational Science (ICTS) at the University of Iowa following an 8 hour overnight fast. The order of visits are as follows and will occur over a period of 7-8 weeks (see TABLE 1 attachment for summary of visits):

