Scheduled safety visit. Subjects will come in at 2 weeks for Visit 5 (approximately Day 14 depending on scheduling) and to have serum salicylate concentrations measured and to confirm no toxicity. The Research Coordinator/Nurse or research staff will review their 2 week side effect log (see attached survey) and survey subjects for any symptoms/side effects and. Subjects will also have serum salicylate concentrations measured at experimental visits 6 and 7.

- VIII.3 Does this study have a plan to have an individual or committee review combined data from all subjects on a periodic basis (such as summary or aggregate safety and/or efficacy data)?

  Yes
  - VIII.4 Describe the plan to review combined data from all subjects, such as summary or aggregate safety and/or efficacy data. Include the following:
    - Describe what data will be summarized and reviewed
    - Describe how frequently data will be reviewed.

The Data Safety Monitoring Plan will consist of a bi-annual independent review of the protocol by [name], Department of Internal Medicine, Division of Nephrology. The PI will provide a bi-annual report to the [name] summarizing the following:

- a) Data on progress of the protocol including subject recruitment, attrition, and minority involvement. Reasons for attrition or other recruiting issues
- b) Data on safety of research participants including unblinded data of serum salicylate, creatinine, ALT/AST concentrations at baseline and from safety visits, data on reasons for any dosing reductions in Salsalate that occurred, and data collected from evening telephone questionnaires for subject symptoms;
- c) Data on compliance in reporting of any adverse events
- d) Data on protocol compliance and any amendments to the protocol
- e) Data on any safety issues that occurred during the 6 month period.
- f) He will confirm that any action that results in the temporary or permanent suspension of the protocol is reported to all the appropriate monitoring bodies such as the CRR protocol committee, IRB, FDA, NIH, or other sponsor, etc.

Every 12 months, the PI will summarize outcome data and provide to [name] for review of the efficacy of treatment intervention on primary outcomes

VIII.5 Will overall safety monitoring be performed by individual(s)/committee at The University of Iowa. (NOTE: If this study involves more than

minimal risk, in most cases these should be individuals who are not members of the study research team.)?

Yes

VIII.6 List names:

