### XI. Data Analysis

### XI.1 Describe the analysis methods you will use, including, if applicable, the variables you will analyze

Statistical analyses. To determine if differences in outcomes are present at baseline between obese pre-diabetic vs. non-pre-diabetic groups, an independent two-sample t-test will be performed. To determine if baseline (pre-intervention) differences exist between salsalate and placebo prediabetic groups after randomization, independent two-sample t-tests will be performed. To test the main hypotheses, a repeated measures ANOVA will be performed in which treatment (salsalate vs. placebo) is the between-subjects factor, and time (pre- vs. post-intervention outcomes) is the within-subjects factor for the primary dependent variables. The critical test for the dependent variable will be the interaction between the within-subjects and betweensubjects factors. Tests for mean contrasts will be used to compare variables of interest pre vs. post Salsalate or placebo. Based on a previous study, we expect small reductions in fasting glucose, triglycerides, LDL cholesterol and possibly systolic blood pressure after Salsalate treatment. Covariates (e.g., variables that change after Salsalate) will be included into the mixed model. Bivariate pearson correlation analysis will be performed on the change in each dependent variable and aforementioned selected covariates after Salsalate.

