### XI.2 Provide the rationale or power analysis to support the number of subjects proposed to complete this study.

Sample size calculations. Sample sizes were calculated based on 80% power at an alpha level of 0.05. Estimated effect sizes for Aim 1 were used for final sample size calculation for obese prediabetic subjects because carotid-femoral PWV is the primary outcome and has the smallest effect size (d) in pilot data of 4 days before vs. after Salsalate. A sample size of 16 subjects per group was determined based on the d of 1.06, based on mean difference in carotid-femoral PWV (-1.0  $\pm$  1.0 m/sec) after Salsalate vs. Placebo.

With a conservative estimated attrition rate of 15-20% and the 2:1 randomization, a total of 20 subjects will be assigned to the Salsalate group, and 10 subjects to the placebo group was determined to be required for the study (total sample size=30). A

sample size of 12 for Aim 2 (FMD) was determined from d of 1.2 for a mean difference in FMD of  $\pm$  2.2 after 4 days Salsalate vs placebo based on previously published work by the PI (19). Because the effect sizes for Aim 1 and 2 are based on preliminary data of 4 days of Salsalate treatment and our proposed study is 4 weeks, we predict that the actual effect sizes will be slight higher because of the longer duration of treatment. Therefore, the proposed study will help determine actual effect sizes for chronic Salsalate therapy for a future larger randomized clinical trial.

A total of 10 obese non-prediabetic control subjects will be recruited to established differences in main outcomes at baseline but will NOT undergo randomization or salsalate/placebo treatment period.

Therefore, total sample size to be enrolled is 40.

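### XI.2 names one primary outcome, but XI.1 tests an unlisted plural set of primary variables with no order or multiplicity rule, so the primary result could be chosen after the data are seen

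*Combined protocol and SAP*

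**What the plan says.** The sample-size section (XI.2) is singular: "carotid-femoral PWV is the primary outcome". It also supplies the only significance level in the documents: "Sample sizes were calculated based on 80% power at an alpha level of 0.05".

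The analysis section (XI.1) is plural. The main hypotheses are tested by repeated measures ANOVA, where "time (pre- vs. post-intervention outcomes) is the within-subjects factor for the primary dependent variables", and "The critical test for the dependent variable will be the interaction between the within-subjects and betweensubjects factors". The variables are neither named nor counted. XI.1 gives no test level, no testing order and no adjustment, and none appears elsewhere.

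The hypotheses in I.5 cover four domains. Hypothesis 1 is "Chronic inflammation inhibition will improve microvascular and large elastic artery function in obese adults with prediabetes"; Hypothesis 2 is "Chronic inflammation inhibition will decrease MSNA and improve baroreflex sensitivity in obese adults with prediabetes".

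VII.B.11 says that there is no separate written protocol, so no further document is available to settle which reading is meant.

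**The concern.** A reader of XI.2 would expect one primary result, for carotid-femoral PWV. A reader of XI.1 would expect several, and could not say which. I.5 offers four domains. XI.2 sizes a second outcome, FMD, and assigns it to Aim 2, although Aim 2 in I.5 is MSNA and baroreflex sensitivity. The microvascular domain alone has more than one candidate measure in VII.E.6: forearm flow responses to acetylcholine at two doses, with and without vitamin C, and retinal vessel widths.

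Since both readings are open, the choice between them can be made once results are known. A positive interaction on any one of these variables could then be presented as support for a main hypothesis. The study is also meant to supply effect sizes for a larger trial, and picking the most favourable of several outcomes from 20 versus 10 subjects would tend to exaggerate the effect carried forward.

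**Working it through.** **Plan's own figures.** XI.2 gives 16 per group for PWV at d = 1.06 and 12 for FMD at d = 1.2, with 80% power and alpha 0.05. Sidedness is not stated; two-sided is assumed. With the normal approximation, n per group = 2(1.960 + 0.842)²/d²:

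- d = 1.06: 15.70/1.124 = 13.97, so 14. A noncentral-t calculation gives 15. The plan says 16.
- d = 1.2: 15.70/1.44 = 10.9, so 11. Noncentral-t gives 12. The plan says 12.

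Both are close to the stated numbers. A one-sided test at d = 1.06 would need only 12, which does not fit. The planning therefore agrees with an unadjusted two-sided 0.05 for each outcome sized.

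**Familywise error.** The documents state none, so this part rests on assumptions:

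1. each variable is tested at two-sided 0.05, carried over from XI.2;
2. all null hypotheses are true;
3. one positive among k variables counts as success;
4. k and the correlation between test statistics are unknown, so both are varied.

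For independent tests the rate is 1 − 0.95^k:

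- k = 2: 1 − 0.9025 = 0.0975
- k = 4: 1 − 0.8145 = 0.1855
- k = 6: 1 − 0.7351 = 0.2649

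For correlated tests, k equicorrelated two-sided z-tests were simulated with 1,000,000 draws per setting.

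| Primary variables | Correlation 0 | 0.5 | 0.7 |
|---|---|---|---|
| 1 (PWV only) | 5% | 5% | 5% |
| 2 (one per aim) | 9.75% | 9.0% | 8.3% |
| 4 (one per domain in I.5) | 18.5% | 15.6% | 13.0% |
| 6 (illustrative: several measures in a domain) | 26.5% | 20.8% | 16.4% |

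**Cost of keeping several primaries.** With two time points, the treatment-by-time interaction is a two-sample comparison of change. Taking d = 1.06 as the standardised between-arm difference, as XI.2's per-group sizing implies, and 20 versus 10 subjects, the noncentrality is 1.06 × √(20 × 10/30) = 2.74 on 28 degrees of freedom. Power is about 75% at two-sided 0.05 and about 53% at 0.05/4 = 0.0125, both before attrition. With 20% attrition (16 versus 8) the figures are about 65% and 41%.

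**The case against.** The strongest reply is that this is a mechanistic pilot and says so. I.4 and I.6 call it a pilot, VII.E.2 justifies the 2:1 allocation by effect-size estimation in the salsalate group, and XI.2 looks ahead to a larger trial. Two hypotheses under two aims can reasonably be tested without a shared alpha, and no section says that success on any one variable supports an overall claim. XI.2 can also be read as naming PWV primary for Aim 1 only, which gives one primary per aim and a rate of about 8–10%.

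Much of this stands. It lowers the weight of the point and rules out a single headline error rate. It does not remove the conflict, because the plan uses confirmatory language (main hypotheses, a critical test, 80% power) without saying which variables that language covers.

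A reader might infer that the trial's false-positive rate simply is 13–19%. The documents do not support that. The range needs four variables, correlations of 0 to 0.7, all nulls true, any-one-positive success and a 0.05 level that XI.1 never states.

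A reader might also take the plural wording elsewhere as proof of several tested primaries. It is not. In VII.E.6 the phrase "to establish prediabetes-related differences in obese adults primary outcomes at baseline" concerns the baseline comparison with the non-prediabetic controls. In VIII.4 the yearly summary "for review of the efficacy of treatment intervention on primary outcomes" specifies no hypothesis test.

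**Conclusion.** The inconsistency holds: one named primary outcome in XI.2, an unlisted plural set in XI.1, and no hierarchy or adjustment to reconcile them. The main consequence is that the primary result is not fixed in advance.

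The size is conditional. Under the four assumptions in the working, the familywise error is about 8–10% for two variables, 13–19% for four and up to about 26% for six. If PWV alone is confirmatory, it stays at 5%. The documents do not determine which case applies. Given the pilot purpose, this is a correction that should be made, not a flaw that undermines the design.

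**What to change.** In XI.1, state that the treatment-by-time test on carotid-femoral PWV is the single primary test at two-sided 0.05, consistent with XI.2. List forearm blood flow, FMD, MSNA, baroreflex sensitivity and the retinal measures as secondary. Report these as between-arm differences with 95% confidence intervals, and interpret them as supportive information for the future trial. The baseline control comparison in VII.E.6 can stay as it is.

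This takes no power from the PWV test. Its cost is one of scope and should be stated openly: Hypothesis 2 and the microvascular part of Hypothesis 1 would no longer have a confirmatory test. That is the investigator's decision. If those outcomes are to remain primary, XI.1 should list each one, with one defined measure per domain, and state a multiplicity adjustment. Bonferroni over four tests would lower power for PWV from about 75% to about 53% before attrition, so the single primary is the cheaper choice at this sample size.

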endothelial cells are documented by cell staining of vWF and nuclear integrity is confirmed using DAPI staining. Once endothelial cells with intact nuclei are identified, they were analyzed using Metamorph Software (Universal Imaging; Downingtown, PA) to quantify the intensity of primary antibody-dependent AlexaFlour488 staining (i.e., average pixel intensity). The number of cells typically recovered from each guide wire results in approximately 50-100 cells per slide. Eight slides and two control cultured human umbilical vein endothelial cell (HUVEC: passage 6-9 processed identically to the sample cells) slides are selected for each staining batch. Values are reported as a ratio of sample endothelial cells to HUVEC average pixel fluorescence intensity to reduce variability between staining batches. A singe technician will be blinded to the identity of the subject during the staining and analysis procedures.

- b) Pulse wave velocity. Carotid-femoral, carotid-brachial, and carotid-radial PWV will be measured non-invasively by recording carotid, femoral, brachial and radial artery pressure waveforms sequentially with an applanation tonometer (Non-invasive Hemodynamics Workstation, Cardiovascular Engineering, Inc.). Pressure waveforms are gated to the ECG R wave in order to calculate the transit time (t) between the foot of the carotid and the respective peripheral (femoral, brachial, radial) waveforms. The carotid-femoral transit distance (CFTD) is estimated between the 2 anatomical sites as the difference between the suprasternal notch (SSN) to carotid (SSN-C) and femoral (SSN-F) sites. Thus, the CFTD is calculated as CFTD= (SSN-F)-(SSN-C) and PWV calculated as CFTD/t. This approach accounts for parallel transmission of the pulse wave up the brachiocephalic and carotid arteries, and simultaneously along the aortic arch using the SSN as a fiducial point where parallel transmission begins (e.g., bifurcation site of aortic arch and brachiocephalic artery). The intra-subject reproducibility of carotid-femoral PWV is excellent with a coefficient of variation of 2.1% for triplicate measurements on non-consecutive days in 7 young adults.

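### Cheap improvement, not an error: the critical test in XI.1 does not use the collected baseline value of the outcome as a covariate

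*Combined protocol and SAP*

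**What the plan says.** XI.1 specifies a repeated-measures ANOVA with treatment as the between-subjects factor, in which "time (pre- vs. post-intervention outcomes) is the within-subjects factor for the primary dependent variables". It then fixes the decisive comparison: "The critical test for the dependent variable will be the interaction between the within-subjects" and between-subjects factors. The baseline measurement therefore enters as one level of the outcome, not as a covariate.

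Two other sentences in XI.1 bear on baseline. On covariates: "Covariates (e.g., variables that change after Salsalate) will be included into the mixed model". On balance between the arms: "To determine if baseline (pre-intervention) differences exist between salsalate and placebo prediabetic groups after randomization, independent two-sample t-tests will be performed".

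The baseline data will exist. Under Order of visits in VII.E.6, "Subjects will undergo experimental testing at baseline and again after the 4-5 weeks of Salsalate or placebo", and randomisation comes near the end of Visit 4, after the baseline measurements. XI.2 names carotid-femoral PWV as the primary outcome. It plans 20 v 10 randomised with 15-20% attrition, and says that "the proposed study will help determine actual effect sizes for chronic Salsalate therapy for a future larger randomized clinical trial".

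**The concern.** With a single pre and a single post value, the treatment-by-time interaction is the two-sample t-test on change scores. That amounts to fixing the coefficient on baseline at 1. ANCOVA estimates the coefficient instead, and so removes the part of the change-score variance that comes from chance differences in baseline. In a trial of 30 subjects allocated 2:1, that part can be appreciable.

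Nothing else in XI.1 fills the gap. The only example of a covariate is a variable that the drug itself moves, which is a post-treatment variable and gives no baseline adjustment. The between-arm baseline t-tests may show an imbalance but adjust nothing.

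What is at stake is precision. The estimate is meant to inform the design of a larger trial, so a narrower interval from data already collected is worth having.

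**Working it through.** **Inputs.** From XI.2: d = 1.06, alpha 0.05, power 80%, 16 per group, 20 v 10 randomised, attrition 15-20%. Derived: 16 v 8 completers, from 20% attrition in both arms. Assumed, because the documents do not say: a two-sided test, d on the change-score scale, and a pre-post correlation rho between 0.5 and 0.95.

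**The plan's own figure.** For d = 1.06, 80% power and two-sided 0.05, the normal approximation gives 14 per group and the t-test 15. Power at 16 per group is 82.7%. The stated 16 is reproduced to within 2. With the same d, the planned test has power 75.2% at 20 v 10 and 64.8% at 16 v 8.

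**Variances.** Let s be the pre SD, k the ratio of post SD to pre SD, and N = n1 + n2, with a common slope in both arms.

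- Change score: s² (1 + k² − 2k·rho)(1/n1 + 1/n2)
- ANCOVA: s² k² (1 − rho²)(1/n1 + 1/n2) × (N − 3)/(N − 4)

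The last factor is the price of estimating the slope: 27/26 = 1.038 at N = 30 and 21/20 = 1.05 at N = 24.

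**Equal SDs (k = 1).** The ratio of ANCOVA to change-score variance is (1 + rho)/2 × (N − 3)/(N − 4). It equals 1 at rho = 2(N − 4)/(N − 3) − 1:

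- N = 30: 52/27 − 1 = 0.926
- N = 24: 40/21 − 1 = 0.905

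Judged on confidence-interval width, which also counts the degree of freedom lost in the t quantile, the break-evens are 0.920 and 0.894. Simulation (200,000 trials per setting) agrees with the variance ratios to within 0.004.

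**Power.** On the ANCOVA scale the effect becomes d × √(2/(1 + rho)); at rho 0.5, for example, 1.06 × 1.155 = 1.22. Simulated power and the variance ratios:

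| rho | Variance ratio, 20 v 10 | Power, 20 v 10 (planned 75.2%) | Variance ratio, 16 v 8 | Power, 16 v 8 (planned 64.8%) |
|---|---|---|---|---|
| 0.5 | 0.78 | 84.9% | 0.79 | 74.9% |
| 0.7 | 0.88 | 80.1% | 0.89 | 69.5% |
| 0.9 | 0.99 | 75.9% | 1.00 | 64.9% |
| 0.95 | 1.01 | 74.6% | 1.02 | 63.7% |

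**Unequal pre and post SDs.** Since 1 + k² − 2k·rho = k²(1 − rho²) + (1 − k·rho)², the change-score variance exceeds the ANCOVA residual variance by (1 − k·rho)², which is never negative. Under common slopes ANCOVA can therefore lose only through the factor (N − 3)/(N − 4), about 4% at N = 30 and 5% at N = 24. The range of rho where it loses does move with k:

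| Post SD / pre SD | ANCOVA less precise, 20 v 10 | ANCOVA less precise, 16 v 8 |
|---|---|---|
| 0.9 | at no rho | at no rho |
| 1.1 | 0.79 to 0.96 | 0.77 to 0.97 |
| 1.2 | 0.69 to 0.91 | 0.67 to 0.92 |

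**Unequal slopes (illustrative, unit SDs).** The direction matters.

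- Slopes 0.6 (salsalate) and 0.9 (placebo): variance ratios 0.98 (20 v 10) and 1.00 (16 v 8), against 0.88 and 0.89 for a common slope at their weighted mean, (2 × 0.6 + 0.9)/3 = 0.7. The gain shrinks.
- Slopes 0.9 and 0.6: ratios 0.89 and 0.90, against 0.935 and 0.945 for a common slope of (2 × 0.9 + 0.6)/3 = 0.8. The gain grows.
- Slopes 0.6 and 0.95: ratios 1.02 and 1.04. ANCOVA is slightly worse.

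**The case against.** The strongest reply is that a change-score analysis of a randomised pre-post design is an accepted, pre-specified choice, and that this is a pilot. That stands. A reader might infer that the planned interaction test is biased or invalid. It is not: it is unbiased over randomisations, and valid when the change variances are equal.

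A reader might also infer that ANCOVA always wins. The documents do not support that, because they give no pre-post correlation. The only reproducibility figure for PWV, "with a coefficient of variation of 2.1% for triplicate measurements on non-consecutive days in 7 young adults", cannot be converted to a correlation without a between-subject SD, so a value high enough to remove the gain cannot be excluded. The break-evens of 0.93 and 0.90 also depend on equal pre and post SDs. If response to the drug varies between subjects and widens the post values, the break-even falls. This part of the objection stands, though the loss remains small.

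Three further points limit the claim. The covariate sentence gives an example, not a closed list, so baseline is unnamed but not ruled out. XI.2 does not say which SD underlies d, and a mean difference of 1.0 with SD 1.0 gives 1.0, not 1.06, so the power figures rest on reading d as a change-score effect. And ANCOVA does not repair unequal variances under 2:1 allocation. With slopes 0.9 and 0.6 at 16 v 8, simulated Type I error was 10.4% for ANCOVA and 11.4% for the change score.

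**Conclusion.** The point holds as an inexpensive gain in efficiency. With equal slopes and equal pre and post SDs, ANCOVA adds about 10 points of power at rho 0.5 and about 5 at rho 0.7. It adds almost nothing near 0.9 and loses about 1 point or less at 0.95. If the post SD is 10-20% larger than the pre SD, the break-even falls to about 0.67-0.79, but under common slopes the variance loss is at most about 4-5%. If the post SD is 10% smaller, ANCOVA is more precise at every rho. Unequal slopes can shrink or enlarge the gain, depending on which arm has the steeper slope.

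It would be tempting to conclude that ANCOVA restores the planned 80% power. It reaches 80% at 20 v 10 only if rho is about 0.7 or lower, and at 16 v 8 it gives about 70% at rho 0.7. The shortfall from applying a per-group size of 16 to a 2:1 split is a separate matter that this change does not cure.

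**What to change.** State in XI.1, before outcome data are seen by arm: *Primary analysis: ANCOVA of the post-intervention value on treatment with the baseline value of the same outcome as covariate; report the adjusted mean difference with 95% CI.* Keep the repeated-measures ANOVA as a supportive analysis, and label any model with post-treatment covariates exploratory. A treatment-by-centred-baseline term can be added as a sensitivity check on equal slopes.

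Timing matters because VIII.4 provides for efficacy review during the trial: "Every 12 months, the PI will summarize outcome data". The wording should be settled before the first such summary. The sponsor can look at the pre-post correlation and SDs in its pilot data beforehand.

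The cost is one degree of freedom, a few sentences in XI.1, and a small precision loss (variance up to about 5% under common slopes) if the correlation is very high or the post SD is larger. If XI.2 is to match, its effect size must be restated for ANCOVA. No new measurements are needed.

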Specifically, chronic activation of the nuclear factor kappa B (NFkappaB), a key pro-inflammatory transcription factor that regulates hundreds of inflammatory genes and is regulated by its upstream activator IkappaB kinase beta (IKKB), is hypothesized to be a central feature of vascular inflammation that promotes atherosclerosis in obesity and diabetes. 5, 6 Moreover, recent evidence strongly links IKKB/NFkappB axis activation in the mediobasal hypothalamus to obesity-mediated hypertension in rodents primarily from enhanced sympathetic nervous system activation. 7 Taken together, these data suggest that the IKKB/NFkappaB axis may be a common molecular target to treat vascular and autonomic dysfunction in obese prediabetic humans.

Salsalate, a non-acetylated salicylate prodrug that has been used for decades to treat chronic inflammatory diseases such as rheumatoid arthritis, inhibits the IKKB/NFkappB pro-inflammatory pathway. 8 Accordingly, we recently demonstrated that acute high-dose salsalate improved vascular endothelial function in older obese adults 5 via reduced vascular NFkappaB. We also found reduced blood pressure, fasting glucose and HOMA score, suggesting favorable effects on autonomic function and insulin sensitivity. Indeed, a recent clinical trial demonstrated improved dysglycemia and HbA1c after 3 months of salsalate therapy in adults with diabetes9, however, there have been no studies

investigating the effects of chronic salsalate administration on cardiovascular and autonomic function in these groups of adults. Therefore, the current pilot proposal will test the central hypothesis that short-term salsalate administration will improve vascular and autonomic dysfunction in obese adults with prediabetes. We chose to study adults with prediabetes rather than overt Type 2 diabetes in order to isolate the efficacy of salsalate on vascular and autonomic dysfunction in the early stages of diabetes without the confounding effects of anti-diabetic medications and advanced diabetic co-morbidities.

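### XI.1 puts variables that salsalate itself changes into the model for the main test, without naming the test that omits them as primary or limiting covariates to baseline values

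*Combined protocol and SAP*

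**What the plan says.** Section XI.1 sets out the main analysis: "To test the main hypotheses, a repeated measures ANOVA will be performed in which treatment (salsalate vs. placebo) is the between-subjects factor". Time, pre versus post, is the within-subjects factor. It continues: "The critical test for the dependent variable will be the interaction between the within-subjects and betweensubjects factors". After a line on mean contrasts, it names what the drug should move: "we expect small reductions in fasting glucose, triglycerides, LDL cholesterol and possibly systolic blood pressure after Salsalate treatment". The next sentence is the covariate rule: "Covariates (e.g., variables that change after Salsalate) will be included into the mixed model". The paragraph closes with a correlation analysis: "Bivariate pearson correlation analysis will be performed on the change in each dependent variable and aforementioned selected covariates after Salsalate".

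No other mixed model is defined. Nothing in XI.1, XI.2 or the rest of the supplied text makes the test without covariates primary, calls the covariate model exploratory, or restricts covariates to baseline values. VII.B.11 answers that no separate written protocol will be submitted, so XI.1 is the only analysis plan supplied.

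**The concern.** Hypotheses 1 and 2 in I.5 ask whether salsalate improves vascular and autonomic outcomes. That is a total effect. XI.1 typifies its covariates by the fact that treatment moves them. If their on-treatment values or changes enter the model, the interaction compares arms as though those variables had moved equally in both. It is then biased for the total effect whenever a covariate is shifted by treatment and also associated with the outcome within arm. The direction depends on the signs of the shift and the correlation.

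Blood pressure shows the difficulty. On earlier salsalate data, I.6 says: "We also found reduced blood pressure, fasting glucose and HOMA score, suggesting favorable effects on autonomic function and insulin sensitivity". Autonomic function is the subject of Aim 2, so adjusting sympathetic nerve activity or baroreflex sensitivity for the change in blood pressure would remove part of the effect under test.

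Two things are at stake. First, two different interaction tests, with and without these covariates, could each be reported as the main result. Second, XI.2 expects that "the proposed study will help determine actual effect sizes for chronic Salsalate therapy for a future larger randomized clinical trial", so a distorted estimate could pass into the next trial's sample size.

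**Working it through.** **The plan's own figure.** XI.2 states: "Sample sizes were calculated based on 80% power at an alpha level of 0.05". Sidedness is not given, so two-sided is assumed. For d = 1.06, the normal approximation 2 × (1.960 + 0.842)² / 1.06² = 13.98 gives 14 per group, and the t test gives 15. The plan states 16, so the input d = 1.06 reproduces to within two subjects.

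**Setting.** XI.2 assigns 20 to salsalate and 10 to placebo, with 15–20% attrition. At 20% attrition, 20 × 0.8 = 16 and 10 × 0.8 = 8 complete. Unadjusted power at d = 1.06 from the noncentral t is 64.8%.

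**Model.** With two time points, the treatment-by-time interaction is a two-sample comparison of change scores. Let T be treatment. The outcome change is Y = d·T + e and the covariate change is M = a·T + u, with unit within-arm SDs and corr(e, u) = ρ. Positive values mean improvement. Regressing Y on T and M gives an expected treatment coefficient of d − ρ·a instead of d. If M is a baseline variable, randomisation makes a = 0 in expectation and the bias vanishes.

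**Assumed inputs.** The documents give neither a nor ρ. The ranges used are a = 0.2 (nearest to the plan's description of the reductions as small) and 0.5–0.8, with ρ = 0.3–0.5. Power and type I error come from 40,000 simulated trials per setting, two-sided 0.05.

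**One covariate, shift and correlation of the same sign:**

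| a | ρ | Estimate | Power | Type I error |
|---|---|---|---|---|
| 0.2 | 0.3 | 1.06 − 0.06 = 1.00 | 61% | 5.2% |
| 0.2 | 0.5 | 1.06 − 0.10 = 0.96 | 66% | 5.6% |
| 0.5 | 0.3 | 1.06 − 0.15 = 0.91 | 52% | 6.3% |
| 0.8 | 0.5 | 1.06 − 0.40 = 0.66 | 34% | 15.3% |

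The two intermediate settings (a = 0.5, ρ = 0.5 and a = 0.8, ρ = 0.3) have type I error of 9.3% and 8.0%. At 0.5–0.8 SD the excess error is almost all in the direction against salsalate.

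**One covariate, opposite signs.** This is less expected, because the named variables should improve, but the list is open. The estimate is 1.12–1.16 at a = 0.2 and runs from 1.21 to 1.46 over a = 0.5–0.8. Under the null, the false-benefit rate is 3.5–4.3% and 5–15% respectively, against a nominal 2.5%.

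**Four covariates, same sign.** Each has correlation 0.2 with the outcome, and 0.3 or 0.5 with each other.
- a = 0.2: estimate 0.97 or 0.99, power about 52%, type I error about 5%.
- a = 0.5: estimate 0.85 or 0.90, power 38% or 43%, type I error 7% or 6%.
- a = 0.5 with no correlation with the outcome, hence no bias: power is already 51–52%. About 65 − 52 = 13 points of the loss are therefore degrees of freedom and collinearity, not bias.

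**Follow-on trial.** For a 1:1 design with 80% power and two-sided 0.05, n per arm is 2 × (1.960 + 0.842)² / d², rounded up. This gives 14 at 1.06, 16–18 at 1.00–0.96, and 19–37 at 0.91–0.66.

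**The case against.** The strongest reply is that XI.1 can be read in stages. The ANOVA and its critical test are fully specified without covariates. Covariates come only later, in a model called by a new name, followed by correlations of changes. That order fits a main test and then an explanatory step. The reading is possible, but the text does not state it, and the plan says the covariates will be included, not that they may be explored.

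A second reply is that the plan expects small reductions, and one covariate shifted by 0.2 SD does little harm. That stands. The larger figures need shifts of 0.5–0.8 SD, which no document supports, and they should be read as the outer part of a range.

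Third, most of the power loss with four covariates at small shifts reflects too many covariates for 24 completers. That also stands, and it is separate from bias.

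Fourth, the calculation takes one model form, covariate change entered as a single regressor. Time-varying values in a mixed model blend within- and between-subject associations and need not give exactly d − ρ·a. The formula is therefore an illustration.

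Fifth, the blood pressure example has limits. XI.1 lists systolic pressure only as possible, and the blood pressure result cited in I.6 came from acute high-dose treatment in older obese adults.

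Finally, unadjusted pre/post contrasts are also planned, so later designers would not be confined to the adjusted estimate. None of these points supplies the missing statement of which test is primary or when the covariates are measured.

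**Conclusion.** The concern holds and should be fixed. As written, XI.1 directs covariates typified by their response to salsalate into the only model described for the main hypotheses, and it sets no order between the tests with and without them. The missing hierarchy is a defect on any reading. The bias is conditional: it arises if on-treatment values or changes enter, which is the plain reading, and it does not arise if only baseline values enter.

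Its size rests on assumed shifts and correlations. For a single covariate it is minor at the small shifts the plan expects. It becomes material at about 0.5 SD and above, and it can run in either direction. Several covariates together would cost roughly 13 points of power in a sample this small, even at small shifts. Confidence in the size is moderate; confidence that the text leaves the point open is high.

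**What to change.** Replace the covariate sentence in XI.1 with wording such as: *The primary test is the treatment-by-time interaction without post-randomisation covariates. Any covariate in the primary model will be a prespecified variable measured before randomisation. Models that include changes in glucose, lipids or blood pressure are exploratory mechanistic analyses.*

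It would also help to say that correlations between covariate changes and outcome changes are computed within arm, since pooling the arms would mix in the treatment shift. The current wording may already mean the salsalate arm only, so this is a clarification and secondary to the main change. Any baseline covariates in the primary model should be few, given about 24 completers.

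The cost is two or three sentences. No data, visits or subjects are added, the repeated measures ANOVA stays as planned, and the covariate analyses can still be run as exploratory work.
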